With NIH funding we previously developed BPG (Brain Powered Games), a CCRT (Computerized Cognitive Rehabilitation Therapy) digital games package for HIV+ school children in the sub-Saharan. As a child plays, BPG gathers game data that can be used for neurocognitive assessment. In this new study, we will further evaluate the capability of BPG as a test for neurodevelopment. In a second phase, we will add an award-winning game developed at the MSU-GEL lab that will train executive function (EF), allowing us to dynamically assess this often-neglected neurocognitive domain in previously tested and well-characterized HIV+, HEU and HUU cohorts of children.

In Study Aim 1 we will adapt and evaluate concurrent and predictive validity of BPG. Here we will evaluate whether BPG as a static (baseline) assessment corresponds to a gold standard of static measures (KABC-II,

TOVA, CogState). Compared to these, we hypothesize that dynamic BPG assessments will be feasible and acceptable, providing for a more sensitive evaluation of brain/behavior function as affected by more proximal factors of HIV exposure, disease and treatment. We also hypothesize that dynamic assessments will be more sensitive to distal developmental risk factors (e.g., SES, nutrition/growth, maternal caregiving quality), measured in early childhood in study cohorts.

In Study Aim 2, we will compare the validity of BPG static and dynamic assessments. Here we will validate BPG static and dynamic assessments with a gold standard of neuropsychological tests previously used with school-age children at our two study sites (Kampala, Uganda and Blantyre, Malawi). Cohorts will be well characterized due to participating in our previous NIH-sponsored HIV clinical trials. We hypothesize that BGP-based static and dynamic assessments will be sensitive to cohorts' prior longitudinal trajectories as affected by proximal and distal risk factors that cause developmental delay and cognitive problems, as measured in our previous clinical trial studies with these cohorts. The executive function game will prove especially sensitive.

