5.0 NEURODEVELOPMENTAL ASSESSMENT PROTOCOL DESIGN

5.1 Overview of Study Design:

[figure not shown]
Static and Dynamic Assessment Process for Each Study Child. Figure 6 provides an overview of study visits and assessments. Following enrollment and physical and medical exams, each child will return to the clinic with their principal caregiver for a half-day of gold standard neuropsychological assessments (KABC-II, TOVA, CogState). At this time the caregiver will complete the Achenbach CBCL questionnaire for school-age children, the Caldwell HOME scale, the SES material possessions evaluation, and the Hopkins Symptom Checklist-25 (caregiver psychological well-being). We will explain assessments and provide instructions in the local language. Study assessments will proceed in two phases. In Phase I, children will be randomized to start BPG trainings (50% of sample) or to a wait-list condition. Within a week after baseline assessment, the full sample of children will be contacted by a field research assistant and facilitate a first BPG session. This first session will be completed by the full sample because it will be considered as an internal performance evaluation session with BPG and will be completed on a tablet, supervised by the field research assistant. This will be done as part of the 50-60 minutes training session on the 5 BPG games (about 10 minutes per game), and will constitute the BPG static assessment. Thereafter, the field research assistant will return with children allocated to the BPG trainings (50% of sample) at a convenient time and supervise BPG training several times per week until 12 training sessions are completed. The 12th session internal evaluation performance measures for the 5 core games and one added EF game will provide the endpoint for BPG dynamic assessment (gain in BPG performance from session 1 to session 12). Because BPG training will occur on a tablet connected to the internet through the mobile network, performance data can be uploaded for analysis via the MSU GEL lab principal server, as done in the Kayunga Uganda CCRT study with BPG ¹.

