Post Testing and 6-month BPG Dynamic Assessment Follow-up. Within 2-4 weeks after completing BPG training and dynamic assessment, the full sample of children and their caregivers will return to the clinic for a full gold standard neuropsychological evaluation as the caregiver once again completes the CBCL. The final step in Phase I of our study process will be when the field research assistant returns with the child one final time after 6 months to administer 1 session of the BPG games to the full sample (corresponding to an internal performance evaluation for one final time). Within 2-4 weeks of this final BPG assessment, all children and their caregivers will return to the clinic for a gold standard neuropsychological evaluation. Our rationale for choosing when to have the final assessment is based on past work: after 6 months without training, the benefits of training may begin to diminish in terms of a slower rate of change in comparison to the rate of change during the training period. This BPG performance change from post training to 6-mo follow-up will provide an additional dynamic outcome for validity analyses.

In Phase 2 of the study we will assess the static and dynamic properties of an executive behavior-focused cognitive rehabilitation game package called Village Builder. In this Phase, children allocated to the wait-list condition will complete 12 sessions of training with Village Builder in a mobile device and facilitated by a research assistant. Within 2-4 weeks of the final Village Builder session, children will attend the clinic for a gold standard neuropsychological evaluation using the same battery of tests as in Phase 1. The last visit of Phase 2 will be 6 months (+/- 4 weeks) after completion of the training, where a final session of Village Builder will be administered (static evaluation) along with the battery of neuropsychological tests. Caregivers will also complete the CBCL, SES and HOME assessments in the same study visits as their children.

Figure 6. Study visits and assessments (numbers for 1 site shown)

PHASE I

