Unlike the existing games in Africa BPG that emphasize vigilance attention, monitoring and working memory, and visual spatial learning and navigation (mazes task), this new Village Builder game will emphasize executive function and reasoning in children. It will be intuitive, culture-fair, non-violent, and designed to be engaging for the computer novice and casual gamer. [name] has served as a consultant on NIH application to develop a touch screen Android Tablet assessment game package for assessment of executive functioning in preschool-age children, called "EF Touch". This app has undergone pilot testing with Kenyan children 4 to 6 years of age.⁶³ Using a model of EF development based on self-control interventions, pro-social values, and validated in early and middle childhood in terms of social and academic outcomes,⁶⁴ [name], [name], and [name] will work together to incorporate the best validated response features of EF Touch (Animal Go/No-Go, Silly Sounds Stroop, Pick the Picture)⁶³ into the new Village Builder EF game. The eventual goal is to compare the dynamic versus static BPG cognitive assessment features when they emphasize attention, memory, and learning tasks and when they emphasize planning and reasoning tasks in school-age children. Both types of BPG games (attention/memory/learning versus planning/reasoning) will also be compared to the gold standard of tests presently validated for the study sites (KABC/TOVA/CogState) in terms of their comparative sensitive to more proximal (HIV exposure and treatment) and distal (nutrition and quality of caregiving and home environment)

risk factors.

By comparing Village Builder executive function (EF) game to the existing Africa BPG package, we can better understand what value it adds in terms of a static and dynamic assessment of brain/behavior function in younger school-age African children. At present, no such CCRT intervention or assessment program exists that has been validated for African children, despite the great importance of EF in frontal lobe brain development at this stage of middle childhood. EF and frontal lobe development are vitally important precursors for future neurocognitive adaptation and function in children affected by HIV (e.g., self-management, impulsivity, planning, treatment adherence, psychosocial adjustment and prosocial behavior) as they age into adolescence and eventually into early adulthood.

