5.6.6 Summary of Procedures by Study visit

The following procedures will be conducted at the screening and enrollment visit of all enrollees

Table 1: Enrollment and Intake Visit(s) for all enrollees

Component	Procedures
Administrative and Regulatory	
 • Assess eligibility • Obtain written informed consent/ assent • Assign a Participant Identification (PTID) Number • Provide reimbursement for study visit
Clinical	
 • Obtain medical history • Conduct a brief physical examination (main organ systems and
Neurodevelopment Assessments	KABC-II TOVA
Caregiver-reported assessments	CBCL HOME
Brain Powered Games	1 st session for treatment condition (e.g. training) and only 1 session for wait list group (e.g. assessment)

*Depending on staff availability and scheduling, enrollment and baseline visits will be done on the same day

Table 2: BPG training visits for 50% of sample

Component	Procedures
Administrative and	
 • Schedule next visit
Brain Powered Games package	
 • Complete 10 sessions (About 2 per week for 6 weeks) of approximately 30-45 min

Table 3: Follow-up Visits for all enrollees

Component	Procedures
Administrative and	
 • Provide reimbursement for study visit

Clinical	
 • Obtain medical history • Conduct a brief physical examination (main organ systems and
Neurodevelopment Assessments	KABC-II TOVA
Caregiver-reported assessments	CBCL HOME
Brain Powered Games	12th session for BPG training group and 1 session for wait list group 1 session at 6-months follow-up for entire sample

Table 4: 12 session trainings of Village Builder (wait-list) and

Component	Procedures
Administrative and	
 • Provide reimbursement for study visit
Clinical	
 • Obtain medical history • Conduct a brief physical examination (main organ systems and
Neurodevelopment Assessments	KABC-II TOVA
Caregiver-reported assessments	CBCL HOME
Village Builder	
 • Complete 12 sessions (About 2 per week for 6 weeks) of approximately 30-45 min

Table 5: Follow-up visits for wait-list group

Component	Procedures
Administrative and	
 • Provide reimbursement for study visit

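### Village Builder is trained only in Phase 2, in wait-list children already exposed to BPG, so comparing its mean gains with BPG's across phases is confounded with period, retest number and carry-over

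*Combined protocol and SAP*

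**What the plan says.** **The comparison.** Section 5.6.5 intends to learn what the executive-function game adds as a static and dynamic measure, "By comparing Village Builder executive function (EF) game to the existing Africa BPG package", and to compare both types of game on their sensitivity to proximal and distal risk factors. Section 3.0 predicts the result: "The executive function game will prove especially sensitive". Section 5.3 lists the game among the exposure variables of interest. Section 5.6.5 also makes pre- to post-training gain on the gold-standard tests a principal performance outcome.

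**The sequence.** Section 3.0 brings the game in later: "In a second phase, we will add an award-winning game developed at the MSU-GEL lab". Under Section 5.1, Phase 2, "children allocated to the wait-list condition will complete 12 sessions of training with Village Builder".

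**Exposure before Village Builder.** Wait-list children have three BPG sessions:
- intake (Section 5.1): "This first session will be completed by the full sample";
- post-training (Section 5.6.6, Table 3): "12th session for BPG training group and 1 session for wait list group";
- six months (same table): "1 session at 6-months follow-up for entire sample".

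Section 5.1 also gives every child the gold-standard battery at intake, after training and after the six-month session.

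**The analysis.** Section 7.1.2 works with intake, 1 and 7 months. It does not mention Village Builder or Phase 2 and has no phase, sequence or carry-over term. The only related adjustment is the number of prior neuropsychological testing sessions, in the model for the 1- and 7-month measures.

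**A conflict.** Section 5.1 counts one added executive-function game in the session-12 measures of the Phase I BPG arm. That does not fit Section 3.0 or the Phase 2 text of Section 5.1.

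**The concern.** The design is a one-way switch: BPG training is observed early in one randomised half, Village Builder training later in the other. Randomisation balances the halves at intake, so selection is not the problem; timing and prior exposure are. The protocol itself treats these mechanisms as real. Section 5.5.1 adjusts for prior testing, Section 5.6.5 uses the Butterfly game to familiarise children with the tablet interface, and Village Builder shares BPG's village motif and animals.

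If Phase 2 gains are set beside Phase I gains, Village Builder could be credited or faulted for what is really maturation, a later retest or earlier play with BPG.

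**Working it through.** **Plan's own figures.** None is given for Village Builder versus BPG. The sample size in Section 7.1.2 rests on cohort differences. With power = Φ(d·√[n₁n₂/(n₁+n₂)] − 1.96):
- HEU vs HUU, 240 vs 240, d = 0.26: Φ(2.848 − 1.96) = 0.81, as stated.
- HIV+ vs either, 120 vs 240, d = 0.31: Φ(2.773 − 1.96) = 0.79, essentially the stated 0.80.

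**Who is in Phase 2.** Section 5.6.1 puts 60 HEU, 60 HUU and 30 HIV+ children on the wait list. Read per site, that is 150, and 2 × 150 = 300 in all.

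**State at the start of training.**

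| | BPG arm | Wait-list, before Village Builder |
|---|---|---|
| Study batteries taken | 1 | 3 |
| BPG sessions played | 0 | 3 |
| Time since intake | about a week | at least 7 months |
| Concurrent untrained group | wait-list | none visible |

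**What the battery changes can identify.** Let g₁, g₂, g₃ be the untrained change (age, period, retest) over intake to post, post to six months, and the Village Builder training window. Let B and V be the training effects of BPG and Village Builder, R the later change specific to the BPG arm, and C the carry-over from three BPG sessions. The expected mean changes are:
- D₁, BPG arm, intake to post: g₁ + B
- D₂, wait-list, intake to post: g₁
- D₃, BPG arm, post to six months: g₂ + R
- D₄, wait-list, post to six months: g₂
- D₅, wait-list, six months to post-Village Builder: g₃ + V + C

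These are five cells (rank 5) for seven unknowns. The cross-phase contrast is

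D₅ − D₁ = (V − B) + (g₃ − g₁) + C.

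It equals V − B if g₃ = g₁ and C = 0, and the data can test neither. Subtracting the wait-list's Phase I change from both sides gains nothing: (D₅ − D₂) − (D₁ − D₂) = D₅ − D₁. A concurrent untrained Phase 2 group would supply g₃, but would still leave V + C − B.

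**Prior-testing covariate.** If carried into Phase 2, it adds the same three Phase I batteries for every child, so it moves with phase. It separates practice only if a common effect per test is assumed, and it covers neither age nor carry-over.

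**Which statistics are exposed.** Suppose a shift a is common to all children.
- Correlation: Corr(X + a, Y) = Corr(X, Y), unchanged.
- Known-group effect size: [(m₁ + a) − (m₂ + a)]/SD = (m₁ − m₂)/SD, unchanged.
- Standardized response mean: (mean change + a)/SD of change, shifted by a/SD.
- Gain scores: shifted by a.

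The exposed statistics are therefore gain scores and response means. Practice or carry-over that differs between children or cohorts can still move the other two.

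**Reach of a cross-phase test.** At 300 vs 300 and SD of change 1, 80% power is reached at (1.96 + 0.842)·√(2/300) = 0.23 SD. A spurious offset of that size would be declared a difference just as often as a real one. This describes the test; it is not an estimate of the bias.

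**Precision within the wait-list half.** HEU vs HUU, 120 vs 120, d = 0.26: Φ(2.014 − 1.96) = 0.52. HIV+ vs either, 60 vs 120, d = 0.31: Φ(1.961 − 1.96) = 0.50. Known-group results for Village Builder therefore need intervals, not just tests.

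**The case against.** **The comparison is of assessments, not of training efficacy.** Much of Section 5.6.5 concerns correspondence and sensitivity to risk factors, for which correlations and known-group effect sizes are the tools. This stands. A reader might infer that Village Builder cannot be compared with BPG at all; the documents do not support that. The response mean (Section 7.1.2) and gain scores (Section 5.6.5) do depend on mean change, so the concern remains for those.

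**The children are not new to the tests.** A reader might assume a retest gain of 0.2 to 0.3 SD from first to second battery and 0 to 0.1 SD from third to fourth, and infer that Village Builder would look 0.1 to 0.3 SD worse than BPG. That is not supported. Section 5.5.1 gives HEU and HUU children, 480 of 600, three earlier KABC-II assessments (Section 5.4 lists the KABC-II at two ages), so for them the study's first KABC-II is not a naive one. Nor is the direction of carry-over known: familiarity could raise the first Village Builder score and shrink the session 1 to 12 gain, or speed learning and enlarge it.

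**An untrained reference exists.** The wait-list's own Phase I change is untrained, so it would be wrong to say there is no comparator. It comes from an earlier period and earlier retests; what is missing is a concurrent one.

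**Some text was not available.** Figure 6, the end of the Table 4 title in Section 5.6.6, the schedule in the appendices and the text between Sections 4.1 and 4.3 could not be read. The study flow chart in Section 4.3 also mentions additional training for underperforming children. A Phase 2 comparator described only there would change this point.

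**The goal is secondary.** Section 5.6.5 describes the comparison as an eventual goal. It is in no numbered objective, nor in the primary outcome or the sample-size basis. This stands and sets the priority.

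**Conclusion.** The concern holds for cross-phase comparison of mean gains: the session 1 to 12 game gain, gold-standard gain scores and response means. In these, the game cannot be separated from age and period, retest number and BPG carry-over, and the planned covariate does not separate them. The documents fix neither the size nor the sign of the bias.

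It holds only weakly for correlations and known-group effect sizes, which change only if practice or carry-over differs between children. A reader might infer that the study's main validation is compromised; it is not, because the BPG correlations at intake, 1 and 7 months do not use Phase 2. The change should be made, but as a matter affecting a secondary conclusion.

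This rests on reading Phase 2 as wait-list only, as the available text states, and on treating Village Builder as absent from Phase I. If the executive-function game in Section 5.1's session 12 is Village Builder, the BPG arm's dynamic measure also contains it, and the confounding remains.

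**What to change.** In Sections 5.1, 5.6.5 and 7:

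1. Make the main Village Builder versus BPG static comparison within the wait-list children (up to 300). Compare the six-month BPG session with Village Builder session 1, both against the same final Phase I battery and the same risk factors, as a paired comparison of correlations and known-group effect sizes. A bootstrap over children gives the intervals. Record the time from that battery to Village Builder session 1, which the available text does not fix.
2. That pairing sets a third exposure to BPG against a first exposure to Village Builder. Add a sensitivity analysis using the intake BPG session against the intake battery, so that both games are first exposures. State that fixed order, age and general tablet familiarity remain.
3. Report cross-phase comparisons of 12-session gains and response means as descriptive only.
4. Do not attribute Phase 2 pre-post battery change to Village Builder training. Show it beside the same children's untrained Phase I change, labelled a non-concurrent reference.
5. Reconcile the executive-function game in the Phase I session-12 measures (Section 5.1) with its Phase 2 introduction (Sections 3.0 and 5.1).

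The cost is protocol and SAP wording and a few analyses of data already planned, with no new visits. The price is a narrower claim about Village Builder training gains.

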5.6.6 Summary of Procedures by Study visit

The following procedures will be conducted at the screening and enrollment visit of all enrollees

Table 1: Enrollment and Intake Visit(s) for all enrollees

Component	Procedures
Administrative and Regulatory	
 • Assess eligibility • Obtain written informed consent/ assent • Assign a Participant Identification (PTID) Number • Provide reimbursement for study visit
Clinical	
 • Obtain medical history • Conduct a brief physical examination (main organ systems and
Neurodevelopment Assessments	KABC-II TOVA
Caregiver-reported assessments	CBCL HOME
Brain Powered Games	1 st session for treatment condition (e.g. training) and only 1 session for wait list group (e.g. assessment)

*Depending on staff availability and scheduling, enrollment and baseline visits will be done on the same day

Table 2: BPG training visits for 50% of sample

Component	Procedures
Administrative and	
 • Schedule next visit
Brain Powered Games package	
 • Complete 10 sessions (About 2 per week for 6 weeks) of approximately 30-45 min

Table 3: Follow-up Visits for all enrollees

Component	Procedures
Administrative and	
 • Provide reimbursement for study visit

Clinical	
 • Obtain medical history • Conduct a brief physical examination (main organ systems and
Neurodevelopment Assessments	KABC-II TOVA
Caregiver-reported assessments	CBCL HOME
Brain Powered Games	12th session for BPG training group and 1 session for wait list group 1 session at 6-months follow-up for entire sample

Table 4: 12 session trainings of Village Builder (wait-list) and

Component	Procedures
Administrative and	
 • Provide reimbursement for study visit
Clinical	
 • Obtain medical history • Conduct a brief physical examination (main organ systems and
Neurodevelopment Assessments	KABC-II TOVA
Caregiver-reported assessments	CBCL HOME
Village Builder	
 • Complete 12 sessions (About 2 per week for 6 weeks) of approximately 30-45 min

Table 5: Follow-up visits for wait-list group

Component	Procedures
Administrative and	
 • Provide reimbursement for study visit
Clinical	
 • Obtain medical history • Conduct a brief physical examination (main organ systems and
Neurodevelopment Assessments	KABC-II TOVA
Caregiver-reported assessments	CBCL HOME

Village Builder	
 • 1 session at 6-months follow-up
-----------------	---

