Achenbach Child Behavior Checklist (CBCL). This is NOT part of the neuropsychological gold standard, but is an important parent-based screening tool for emotional and behavioral problems observed in the child. The CBCL is important to assess when a child's social environment is enriched by adult oversight in game assessment and training, reflecting a collateral training benefit.²¹ the CBCL has been translated and adapted in our severe malaria research in Kampala⁵³ and Blantyre^{54,55} and structure validated for use with HIV-affected children³⁵ for the PROMISE ND study and pediatric HIV research in Uganda,^{56,57} and in CCRT intervention studies in Uganda.^{5,6,26} Our principal outcomes are Internalizing, Externalizing, and Total symptoms.

Quality of Home Environment and Caregiving. We will use the middle childhood version of the Caldwell Home Observation for the Measurement of the Environment (HOME) validated for use as an important distal measure predictive of our gold standard assessments.^{58,59} The HOME assesses the stimulation and learning opportunities offered by the child's home environment. Along with HOME, we will also use a socioeconomic evaluation scale of physical quality of the home environment (SES score) also used with Ugandan children and sensitive to long-

term (distal) neurocognitive outcomes such as the KABC-II.⁶⁰

Hopkins Symptom Checklist -25 items. The HSCL is a 25-item self-response questionnaire that will be used to evaluate depression and anxiety symptoms in caregivers .This questionnaire has shown adequate performance in Ugandan populations ^{34, 36}. Questions are scored in a severity scale from 1 to 4, with higher scores indicating more symptoms of distress.

5.6.4 Overview of CD4+ T-cell counts, immune activation, and viral load assessments (HIV cohort only)

[figure not shown]

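### Allocation precedes the baseline BPG session, which Table 1 labels differently by arm: release allocation after session 1 and make that session identical for all children

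*Combined protocol and SAP*

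**What the plan says.** **Order of events.** Section 5.1 states: "In Phase I, children will be randomized to start BPG trainings (50% of sample) or to a wait-list condition". The next step is the first game session: "Within a week after baseline assessment, the full sample of children will be contacted by a field research assistant", who facilitates it. Arm is thus assigned, and apparently known, before session 1. No date of assignment is given, so it is unclear whether arm is also known at the intake battery.

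**Role of session 1.** According to 5.1, "This first session will be completed by the full sample because it will be considered as an internal performance evaluation session with BPG", done on a tablet under the field assistant's supervision, "and will constitute the BPG static assessment". The same section defines the dynamic measure as the gain from session 1 to session 12. The field assistant then returns only to the children allocated to BPG training.

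**Table 1 (5.6.6).** The same session appears as a first "session for treatment condition (e.g. training) and only 1 session for wait list group (e.g. assessment").

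**Assignment (5.6.1).** Random numbers are drawn within each cohort, with the first half going to BPG. The same paragraph also sends the first child to BPG and the next to the wait list. No concealment step is described.

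**Masking and analysis.** The text available says nothing on masking of those who give KABC-II, TOVA and CogState. The covariates listed in 7.1.2 do not include training arm.

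**The concern.** One measurement carries two of the study's main quantities: the static score and the origin of the dynamic gain. It is taken after allocation, by someone who can know the arm and who will go on to train only half of the children. One table calls it training in that half and assessment in the other.

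If the assistant helped or encouraged future trainees more at session 1, the static score would not be the same measurement in the two arms. The trained arm's gain would also start from a raised base. Aims 1 and 2 rest on comparing static with dynamic assessment, and 7.1.2 summarizes change with the standardized response mean (SRM) and Guyatt's SRM. A first exposure to the games cannot be repeated, so a compromised session 1 cannot be recovered later.

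**Working it through.** **1. The plan's own figure.** The only design calculation (7.1, sample sizes) compares HIV cohorts, not arms. Normal approximation: power = Φ(d·√[n₁n₂/(n₁+n₂)] − 1.96).
- HEU vs HUU, d = 0.26, 240 per cohort: 0.26·√120 = 2.848, giving power 0.813 (233 per cohort suffice for 0.80).
- HIV vs HEU or HUU, d = 0.31, 120 vs 240: 0.31·√80 = 2.773, giving power 0.792, just under the stated 0.80.

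The figures reproduce within tolerance and are not in dispute here.

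**2. Is conduct by arm prescribed?** Side by side:
- Section 5.1: one evaluation session for the full sample, five games at about 10 minutes each, set within a 50–60 minute training session.
- Table 1: training in one arm, assessment in the other.
- Table 2: BPG training sessions of 30–45 minutes.

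The labels conflict and no single length or script is given. No passage sets out a different procedure by arm.

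**3. Can the arm be known at session 1?** Yes. In 5.1 allocation comes first. Under the alternation in 5.6.1, the previous child's arm reveals the next child's.

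**4. Effect on the gain.** Let the trained arm's session 1 score be shifted by b and its session 12 score by c.
- Gain = S₁₂ − S₁, so the gain shifts by c − b.
- SRM shifts by (c − b)/SD of change.
- If the help has no effect at session 12 (c = 0), the shift is −b, in full. If it persists equally (c = b), the shift is zero.

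The documents give no value for b or c.

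**5. Effect on the pooled correlation.** Two equal arms (300:300 from 5.6.1: 60 + 60 + 30 per arm per site, two sites), within-arm correlation r, and arm shifts dx in BPG and dy in the criterion, in within-arm SD units:

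pooled r = (r + dx·dy/4) / √[(1 + dx²/4)(1 + dy²/4)]

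Assumed shifts, r = 0.40:
- dx = 0.3, dy = 0: 0.40/√1.0225 = 0.396. (At 0.2 SD, 0.398; at 0.5 SD, 0.388.)
- dx = dy = 0.3: 0.4225/1.0225 = 0.413. (At 0.2 SD, 0.406; at 0.5 SD, 0.435.)
- dx = 0.3, dy = −0.3: 0.3775/1.0225 = 0.369.

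The standard error of r = 0.40 with 600 children is about (1 − 0.16)/√599 = 0.034. Each 0.3 SD case moves r by less than that. A value close to a cut-off can still change class: r = 0.39 (weak in 7.1.2) becomes 0.4125/1.0225 = 0.403 (moderate) with 0.3 SD shifts in both.

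**6. Would a shift be noticed?** With 300 per arm, the arm difference detectable with 80% power (two-sided 0.05) is (1.960 + 0.842)·√(2/300) = 0.23 SD. Smaller baseline differences could easily pass unseen.

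**The case against.** The strongest reply is that 5.1 governs. It prescribes one session for everyone and explains why everyone takes it. Table 1 may mean no more than first of twelve versus the only one at that stage. The assistant's stated role is to supervise, each game has its own visual tutorial (5.6.5), and the account of teaching and feedback in the background section describes dynamic assessment in general, not session 1. BPG scores go from tablet to server (6.0), and TOVA and CogState are computerized, so little is left to a rater. The primary outcome (5.3) is a correlation, 7.1.2 plans no trained-minus-wait-list contrast, and allocation is 50:50 within each cohort, so an arm-wide shift is balanced across the HIV comparisons.

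Most of this stands. A reader might infer from Table 1 that half of the sample is coached at baseline; the documents do not say so. A reader might also infer that testers are unmasked. The text is silent, parts of it are not available here, and a Manual of Operations is listed among the abbreviations.

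What remains is the order of events. Allocation precedes an unrepeatable baseline, the assistant can know the arm, and two sections describe the session differently. Automatic recording prevents scoring bias, but not an effect of help or encouragement on the child's play.

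**Conclusion.** The point holds as a weakness in the stated order and wording, not as demonstrated bias. The plan allows session 1 to be conducted with knowledge of arm and describes it inconsistently.

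Its size depends on the quantity. The gain and its SRM are directly exposed: a session 1 shift passes through in full with opposite sign unless it persists to session 12. How large that shift would be is unknown, so no claim that the SRM would fall from one interpretive band to another is supported. The pooled primary correlation is hardly exposed: from 0.40 to between 0.396 and 0.413 under 0.3 SD shifts, or 0.369 if the two shifts were opposed. Those shifts are assumptions for illustration. At intake the BPG-only case is the more natural one, because 5.1 places the battery before session 1.

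Unspecified masking matters mainly for the examiner-administered KABC-II. A reader might extend the concern to the caregiver-completed CBCL, which 5.6.3 describes as "reflecting a collateral training benefit". That does not carry the point: the CBCL is expressly outside the gold standard, caregivers' knowledge of training is inherent in a wait-list design, and the phrase is a rationale, not an analysis rule.

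**What to change.** - **Sections 5.1 and 5.6.1:** release each child's allocation only after the intake battery and BPG session 1 are complete. Assign from the random-number list and delete the sentence describing alternation.
- **Section 5.6.6, Table 1:** reword to agree with 5.1, so that session 1 is the same standard assessment in both arms, with one script and one duration. Reconcile the session lengths given in 5.1 and Table 2.
- **Section 5.6.3:** state that KABC-II testers are not told the child's arm, where existing staffing allows. The documents give no staffing numbers, so strict separation of testers from field assistants is not assumed to be free.

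The cost is protocol wording and a later release of the list. The small downside is that training visits can be scheduled only after session 1. Sample size and planned analyses are unchanged.
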